#### 7.2 Subject Screening and Informed Consent

As patients are being scheduled for primary or revision unilateral THA, the Principal Investigator or a trained designee at each of the sites will conduct a preliminary screen to determine if the patient meets general requirements for the study. If a patient appears to be eligible, delegated staff will offer study participation to those patients. Having explained the study purpose to the Subject, the Investigator or trained designee shall offer to answer any of the Subject's questions and confirm the Subject understands the following points of the study:

4 MAR 2022; Version Rev 3 DSJ-2019-02 Confidential

- The purpose of the study
- The potential risks or adverse events that are posed by their treatment
- The potential risks or adverse events related to study participation
- Possibility of failure and the need for subsequent treatment(s)
- Alternative procedures/treatments available to the Subject
- Requirements of the study including rehabilitation and follow-up visits
- All the Subject's rights as a participant in the clinical investigation

If the Subject then agrees to participate, his or her willingness must be documented via his/her name, signature and date on the REB's approved ICD and this document countersigned and dated by the person taking consent. The signed ICD will then be placed into the Subject's Medical Record, or study file. Screening, consenting and enrollment are illustrated in Figure 7-1.

The Principal Investigator is responsible for ensuring that no Subject will be included in the study without adequate informed consent. Failure to obtain and properly document this process is in violation of applicable regulations, the Declaration of Helsinki and this study protocol. All ICDs must have approval by the responsible REB. Consent of a Subject needs to come from the Subject themselves and be documented on an ICD.

After Informed Consent, study Subjects will be defined as 'enrolled'. Each enrolled Subject will be assigned a unique Subject identification number by the database. Each Subject will be identified by site or surgeon number (e.g. 01, 02) followed by -001 for the first Subject, -002 for the second Subject and so on. Together the site/surgeon number and the Subject number will comprise the unique Subject ID. This unique identifier will be recorded in the Subject's ICD, medical record and the Screening and Enrollment Log.

4 MAR 2022; Version Rev 3 DSJ-2019-02 Confidential Page **18** of **47** TV-eFRM-02920

#### Figure 7-1 Screening and Enrollment Process

4 MAR 2022; Version Rev 3 DSJ-2019-02 Confidential Page **19** of **47** TV-eFRM-02920

## 8 STUDY PROCEDURES

#### 8.1 **Pre-Operative (-90 days to Day of Surgery)**

Following informed consent and eligibility verification, the Subject will have the following preoperative health and functional status evaluations:

The Subject's orthopaedic medical history and current diagnoses will be documented. Data collected will include but is not be limited to:

- Age, gender, height and weight
- History of concurrent or previous medical issues
- History of previous treatment to the index hip
- Harris Hip Score
- HOOS Jr.
- Radiographs
  - AP Femur\*
  - o Lateral

\*The AP Femur is the preferred view at all time points; however, an AP Pelvis will also be accepted.

The information collected from the 'Pre-Op' visit will be populated on the appropriate eCRFs as indicated in the Time and Events Table (Section 3.2). If pre-operative radiographs of sufficient quality were obtained within 270 days of surgery, then they do not need to be repeated just for the purpose of this study.

#### 8.2 Operative (Day 0)

Each Subject will receive a DePuy femoral stem with a polished neck in combination with a DePuy PINNACLE® acetabular cup. All Subjects will receive a PINNACLE® DM metal liner and a BI-MENTUMTM ALTRX® Dual Mobility Polyethylene Liner. Either metal or ceramic heads may be used; however, compatibilities must align with product labeling. Please note since revisions of existing THAs are acceptable to enroll into this study, variations in what is implanted will occur, however Subjects must receive the PINNACLE® DM metal liner and a BI-MENTUMTM ALTRX® Dual Mobility Polyethylene Liner. If the surgeon determines intraoperatively that there exists insufficient bone quality to support the implantation of the construct that Subject will be withdrawn from the study. Subjects that are withdrawn pre-operatively or intra-operatively will be replaced in order to have a minimum of 30 and up to 45 Subjects implanted with the study devices.

Each surgeon shall perform the surgical approach they are most comfortable with and have the greatest expertise.

Implant sizing shall be performed as per the surgeon's discretion for each individual Subject and will not be standardized between sites. Approximately 5-10 tantalum beads will be placed into the

4 MAR 2022; Version Rev 3 DSJ-2019-02 Confidential Page **20** of **47** TV-eFRM-02920 acetabulum. Bead placement will be standardized across study sites to reduce the possibility of unuseable RSA exams resulting from poor bead spacing or bead occlusion.

Any intra-operative adverse events will be captured as well as details of the surgery and implants/components used. The information collected from the 'Operative' time-point will be populated on the appropriate eCRFs as indicated in the Time and Events Table (Section 3.2).

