#### 6.2 Exclusion Criteria

Subjects will be excluded from participation in the study if they meet any of the following criteria:

- 1. Individuals have active local or systemic infection.
- 2. Individuals who have loss of musculature, neuromuscular compromise or vascular deficiency in the affected limb rendering the procedure unjustified.
- 3. Individuals with poor bone quality, such as osteoporosis, where in the surgeon's opinion, there could be considerable migration of the prosthesis or a significant chance of bone fracture and/or the lack of adequate bone to support the implant(s).
- 4. Individuals with Charcot's or Paget's disease.
- 5. Individuals who, in the judgement of the investigator, would not be a candidate for protocol allowable components to be used for their THA.
- 6. Women who are pregnant or lactating.
- 7. Individuals who have had a contralateral hip that was implanted less than 6 months prior to the time of consent into this study or individuals that expect to have a contralateral hip implanted in the 6 months following the time of consent into this study.
- 8. Individuals that have amputations in either leg that would impact rehabilitation following surgery.
- 9. Individuals who are bedridden per the Investigators determination
- 10. Individuals that have participated in a clinical investigation with an investigational product (drug or device) in the last three months.
- 11. Individuals currently involved in any personal injury litigation, medical-legal or worker's compensation claims.

4 MAR 2022; Version Rev 3 DSJ-2019-02 Confidential

- 12. Individuals, in the opinion of the Investigator, who are drug or alcohol abusers or have a psychological disorder that could affect their ability to complete patient reported questionnaires or be compliant with follow-up requirements.
- 13. Individuals diagnosed and taking prescription medications to treat a muscular disorder that limits mobility due to sever stiffness and pain such as fibromyalgia or polymyalgia.
- 14. Subject has a medical condition with less than 2 years life expectancy.
- 15. Individual has a BMI  $\geq$  45 kg/m^2.
- 16. Individuals who require revision arthroplasty and have a well-fixed non-DePuy Synthes femoral stem or a well-fixed DePuy Synthes femoral stem that does not have a polished neck

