#### 8.7 Radiostereometric Analysis (RSA)

The RSA analysis will be the responsibility of the Canadian RSA Network. In summary, model based RSA software (RSAcore, Leiden, Netherlands) will be used for analysis, employing computer-models of the DePuy Synthes implants and inserted beads representing the bone rigid body. A central analysis service will be employed to analyze anonymized radiographs in a standard manner. DePuy Synthes will provide production CAD models as required for this analysis.

Three-dimensional migration measurements will be made of the acetabular shell relative to the bone beads. The 6-week examination will be used as reference against which the 3-month, 6-month, 1-year and 2-year post-operative exams will be compared. Results obtained from the model based RSA software will be changes from the 6-week (baseline) examination and will report the following at 3 months, 6 months, 1 year and 2 years:

- X, Y and Z translation measurements in mm from baseline;
- X, Y and Z rotation measurements in degrees from baseline;
- Maximal total point motion (one measurement in mm of maximal migration).

In a subgroup of Subjects, a second baseline will be defined as the result collected prior to discharge. For these Subjects, the translation, rotation and maximal total point motion will be reported at 6 weeks, 3 months, 6 months, 1 year and 2 years. This sub-analysis will determine the approximate magnitude of migration that occurs between the time of surgery and 6-weeks post-operative. Three-dimensional migration of the PINNACLE® Acetabular Shell shall be determined from the software.

Linear head penetration (in mm) will be performed by examining the change in distance between the center of the femoral head and the center of the acetabular shell between the 6-week (baseline) exam and the 1 year and 2 year exams. The femoral head center is determined by fitting a CAD sphere to the articular region of the femoral head (ignoring the trunnion area). The acetabular shell center is determined in a similar manner but also uses the silhouette of the cup face to determine its' center point.

4 MAR 2022; Version Rev 3 DSJ-2019-02 Confidential

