#### **11.2 Treatment Assignment**

Subjects enrolled will undergo THA using the study devices listed in Section 5.5.

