#### Per Protocol (PP) Analysis Set

The Per Protocol (PP) Analysis Set will be a subset of Safety Set Subjects who have no major protocol violations that exclude them from analyses, and who have a baseline RSA exam and at least one post-baseline RSA exam. Subjects will be analyzed according to the actual treatment (surgical approach) received during of the study.

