#### **11.6.1 Primary Endpoint**

The primary endpoint is the RSA-measured mean superior cup migration (Y translation in mm) at 2 years.

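### For revision subjects, section 8.2 is inconsistent on whether a new PINNACLE shell is implanted, and no analysis rule keeps a retained shell out of the primary migration mean

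*Combined protocol and SAP*

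**What the plan says.** Section 8.2 opens with a rule for everyone: "Each Subject will receive a DePuy femoral stem with a polished neck in combination with a DePuy" PINNACLE acetabular cup. Section 11.2 agrees: "Subjects enrolled will undergo THA using the study devices listed in Section 5.5", and the cups are among the devices in 5.5.

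Later in the same paragraph, 8.2 makes an allowance for revisions: "since revisions of existing THAs are acceptable to enroll into this study, variations in what is implanted will occur, however Subjects must receive the" dual mobility metal liner and the polyethylene liner. Neither the cup nor the stem is repeated in that minimum.

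Of the components already in place, eligibility addresses only the stem. Exclusion 16 in section 6.2 removes "Individuals who require revision arthroplasty and have a well-fixed non-DePuy Synthes femoral stem", and also those with a well-fixed DePuy Synthes stem lacking a polished neck. No criterion mentions a shell already in place.

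The outcome concerns the shell. Section 8.7 states: "Three-dimensional migration measurements will be made of the acetabular shell relative to the bone beads". Section 11.6.1 states: "The primary endpoint is the RSA-measured mean superior cup migration (Y translation in mm) at 2 years". Section 5.1 sets the objective as migration in the two years after implantation, and sections 8.4 and 8.7 take the 6-week exam as reference.

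Under section 11.5 the Per Protocol set is drawn from "Safety Set Subjects who have no major protocol violations that exclude them from analyses, and who have a baseline RSA exam" and at least one later exam. Section 11.12.1 adds only that 6-week and 2-year data exist. The only breakdown in section 11.9 is by surgical approach.

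**The concern.** The two sentences of 8.2 give different answers on whether a revision subject must receive a new cup. If a subject kept a PINNACLE shell and received only the liners, the follow-up clock would start at the index surgery, not at implantation of the shell. The migration value would then not measure what section 5.1 sets out to estimate, whatever its size.

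The study tests no hypothesis, so the estimate is its product. Section 4.2 wants baseline migration values for judging future products, section 11.12.4 compares them with DSJ_2018_02, and section 11.14 uses a 1-year summary to support regulatory submissions. If retained shells move little, including them makes the construct look more stable than a newly implanted one. The same would apply to the 3-month to 1-year profile and to the other shell translations, rotations and maximal total point motion. Enrolling more subjects would not remove the bias. A split by primary versus revision would not fully remove it either, because the revision group could still mix new and retained shells.

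**Working it through.** **Can a retained shell reach the primary mean under the text as written?**

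1. Eligibility. Revision surgery, failed previous hip surgery and dislocation risk all qualify (sections 3.1 and 6.1). No exclusion names a retained shell.
2. Surgery. The lead sentence of 8.2 and section 11.2 point to a new cup. They also point to a new stem, yet exclusion 16 by implication lets a well-fixed polished-neck DePuy stem stay. The requirement to receive each component is therefore not literal for revisions, and the revision sentence restates only the liners.
3. Measurement. Beads go into the acetabulum at the index surgery (8.2), so a retained shell could be measured by RSA.
4. Analysis. Sections 11.5, 11.9 and 11.12.1 contain no condition or split on when the shell was implanted.

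Entry is not excluded at any step, and it is not expressly permitted at any step.

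**The plan's own precision figure.** Section 11.8 gives SD = 0.2 mm and N = 30. The margin is 2 × 0.2/√30 = 0.0730 mm, as stated. With z = 1.96 it is 0.0716 mm; with t on 29 df, 0.0747 mm.

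**Size of a possible dilution.** Let m be the mean for newly implanted shells and f the retained fraction among analysed subjects. Assume that retained shells migrate 0 on average.

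Reported mean = (1 − f) × m + f × 0 = (1 − f)m, so the understatement is f × m.

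The documents give neither f nor m, so both are shown over an assumed range. The understatement is in mm:

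| Assumed m (mm) | f = 3/30 (10%) | f = 6/30 (20%) | f = 10/30 (33%) | f at which it equals 0.073 mm (0.073/m) |
|---|---|---|---|---|
| 0.1 | 0.010 | 0.020 | 0.033 | 73% |
| 0.2 | 0.020 | 0.040 | 0.067 | 37% |
| 0.3 | 0.030 | 0.060 | 0.100 | 24% |

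Section 11.12.4 defines the historical difference as PINNACLE minus PINNACLE DM. Lowering the DM mean by f × m raises that difference by the same amount.

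**Would the confidence interval reveal it?** With an assumed SD s among retained shells, the mixture variance is (1 − f) × 0.2² + f × s² + f(1 − f)m². At f = 10/30:

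- m = 0.1 and s = 0.05 mm give an SD of 0.172 and a margin of 0.063 mm.
- m = 0.3 and s = 0.1 mm give an SD of 0.224 and a margin of 0.082 mm.

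Both lie close to 0.073 mm, so the width of the interval would give little warning.

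**The case against.** A reader might infer that section 8.2 lets revision subjects keep a fixed shell, that such cases are eligible and no protocol violation, and that the primary mean is therefore biased. The documents do not support that.

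- No section permits shell retention. The lead sentence of 8.2 and section 11.2 say the opposite. Section 8.2 also sets its target of 30 to 45 in terms of subjects implanted with the study devices, and exclusion 5 removes people unsuited to the allowed components.
- The allowance for revisions has ordinary explanations: a retained polished-neck stem, or the revision cups, revision stems and head options in Table 1 and Appendix A. Restating the liners may only reflect that they define the study article.
- A liner-only conversion could count as a deviation under section 14.3. Whether it would be a major violation that removes the subject from the Per Protocol set is not defined. Sections 11 and 11.9 leave derivation and analysis detail to a separate SAP.
- The size rests on assumed inputs. The 0.2 mm in section 11.8 is an SD, not an expected mean. Migration is counted from 6 weeks, so movement before then is outside the primary endpoint for every subject, and the contrast between new and retained shells may be smaller than assumed.
- The intervals and historical tests are exploratory.

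All of this stands, and it limits the point to an ambiguity with an unknown and possibly zero effect. It does not remove the inconsistency within 8.2 or the missing analysis rule. Exclusion 16 already shows that the wording on what each subject receives cannot be literal in revisions, and an undefined major violation is not a dependable safeguard for the primary mean.

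**Conclusion.** The point holds as an inconsistency and a gap. Section 8.2 gives two answers for revision subjects, and nothing in the eligibility criteria, analysis sets or planned breakdowns keeps a retained PINNACLE shell out of the primary mean. Whether any such subject is enrolled cannot be told from the documents.

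If some are, and if retained shells migrate about 0, the mean shrinks by the factor (1 − f). Over the assumed range the understatement runs from 0.01 mm, well below the stated 0.073 mm margin, to 0.10 mm, above it. It is zero if f = 0. Both the direction and the size depend on the near-zero assumption. The mismatch with the objective does not, because a retained shell's value does not describe the two years after its implantation. Confidence is moderate. The correction should be made because it is cheap and changes no result if no shell is retained.

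**What to change.** 1. Reconcile the lead sentence of 8.2 with its revision sentence, and both with 11.2, so that the text states whether every subject receives a new PINNACLE shell. No clinical rule on keeping or replacing shells is proposed here.
2. In 11.5 and 11.12, define the population for all shell-migration endpoints, primary and secondary, and for their DSJ_2018_02 comparisons, as subjects whose PINNACLE shell was implanted at the index surgery.
3. Summarise any retained-shell subjects separately. Keep them in the Safety set and in the functional-score summaries.

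The cost is one sentence in the analysis-set definition and one derived flag. Section 8.2 already has the implanted components recorded, so no new data are needed.

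The downside is that retained-shell subjects would not count toward the 30 analysable for RSA. If 3, 6 or 10 of 30 were set aside, the margin at SD 0.2 mm would become 2 × 0.2/√27 = 0.077, 2 × 0.2/√24 = 0.082 or 2 × 0.2/√20 = 0.089 mm. Enrolment of up to 45 leaves some room to absorb this, although that allowance is meant for attrition.

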#### 8.3 **Prior to Discharge (Day 1 to Discharge)**

Subjects will undergo the standard of care for total hip arthroplasty at the participating sites, including bandaging, anti-coagulation, antibiotic and/or physiotherapy protocols. Device and procedure-related adverse events will be collected.

For clinical sites with the ability to perform immediate post-operative RSA exams, Subjects at these sites will undergo a model-based RSA examination prior to discharge from the hospital. RSA radiographs shall be obtained with Subjects in a supine position. A duplicate RSA exam will be conducted at this time to calculate intra-Subject measurement error.

The information collected from the 'Prior to Discharge' time-point will be populated on the appropriate eCRFs as indicated in the Time and Events Table (Section 3.2).

#### 8.4 6 Weeks (Day 28-56)

All Subjects will undergo a model-based RSA examination. For all sites, the 6-week exam will be used as the reference examination. RSA radiographs will be obtained with Subjects in a supine position. If not performed earlier, a duplicate RSA exam will be conducted at this time-point to calculate the intra-Subject measurement error.

Additionally, the Subject will have the following health and functional status evaluations:

- Harris Hip Score; ROM optional
- Hip Evaluation
- HOOS Jr.
- Forgotten Joint Score
- Adverse Events (if applicable)
- Radiographs
  - o AP Femur
  - o Lateral

The information collected from the '6 Week' visit will be populated on the appropriate eCRFs as indicated in the Time and Events Table (Section 3.2).

#### 8.5 3 Month, 6 Month, 1 Year and 2 Year Visits

The Subject will have the following health and functional status evaluations:

4 MAR 2022; Version Rev 3 DSJ-2019-02 Confidential

Page 21 of 47

- Harris Hip Score
- Hip Evaluation
- HOOS Jr.
- Forgotten Joint Score
- Adverse Events (if applicable)
- Radiographs
  - AP Femur
  - o Lateral
- RSA Exam (supine position)

The information collected from these visits will be populated on the appropriate eCRFs as indicated in the Time and Events Table (Section 3.2).

#### 8.6 Unscheduled Visit

An unscheduled visit is to be documented on an Unscheduled Visit eCRF/CRF when:

1. A Subject returns for an additional visit during a study visit interval as described in Table 3.2

#### - Time and Events.

2. A Subject returns between study visit intervals

If a Subject requires an additional visit during a study interval, and is seen by one or more persons listed on the Delegation of Authority Log, then the following information shall be repeated:

- Harris Hip Score
- Hip Evaluation
- HOOS Jr.
- Forgotten Joint Score
- Adverse Events (if applicable)

If a Subject has an unscheduled visit after the 6 week interval (outside defined protocol window), with one or more persons listed on the Delegation of Authority Log then the following information shall be collected:

- Harris Hip Score
- Hip Evaluation
- HOOS Jr.
- Forgotten Joint Score

4 MAR 2022; Version Rev 3 DSJ-2019-02 Confidential Page **22** of **47** TV-eFRM-02920

- Adverse Events (if applicable)
- Radiographs
  - o AP Femur
  - o Lateral
- RSA Exam (supine position) if RSA Exam was not conducted in-window for previous visit. If Subject is seen multiple times outside of the same defined protocol window, only one RSA Exam is required.

#### 8.7 Radiostereometric Analysis (RSA)

The RSA analysis will be the responsibility of the Canadian RSA Network. In summary, model based RSA software (RSAcore, Leiden, Netherlands) will be used for analysis, employing computer-models of the DePuy Synthes implants and inserted beads representing the bone rigid body. A central analysis service will be employed to analyze anonymized radiographs in a standard manner. DePuy Synthes will provide production CAD models as required for this analysis.

Three-dimensional migration measurements will be made of the acetabular shell relative to the bone beads. The 6-week examination will be used as reference against which the 3-month, 6-month, 1-year and 2-year post-operative exams will be compared. Results obtained from the model based RSA software will be changes from the 6-week (baseline) examination and will report the following at 3 months, 6 months, 1 year and 2 years:

- X, Y and Z translation measurements in mm from baseline;
- X, Y and Z rotation measurements in degrees from baseline;
- Maximal total point motion (one measurement in mm of maximal migration).

In a subgroup of Subjects, a second baseline will be defined as the result collected prior to discharge. For these Subjects, the translation, rotation and maximal total point motion will be reported at 6 weeks, 3 months, 6 months, 1 year and 2 years. This sub-analysis will determine the approximate magnitude of migration that occurs between the time of surgery and 6-weeks post-operative. Three-dimensional migration of the PINNACLE® Acetabular Shell shall be determined from the software.

Linear head penetration (in mm) will be performed by examining the change in distance between the center of the femoral head and the center of the acetabular shell between the 6-week (baseline) exam and the 1 year and 2 year exams. The femoral head center is determined by fitting a CAD sphere to the articular region of the femoral head (ignoring the trunnion area). The acetabular shell center is determined in a similar manner but also uses the silhouette of the cup face to determine its' center point.

4 MAR 2022; Version Rev 3 DSJ-2019-02 Confidential

